## 10 SUPPORTING DOCUMENTATION AND OPERATIONAL CONSIDERATIONS

### 10.1 REGULATORY, ETHICAL, AND STUDY OVERSIGHT CONSIDERATIONS

#### 10.1.1 INFORMED CONSENT PROCESS

##### 10.1.1.1 CONSENT/ASSENT AND OTHER INFORMATIONAL DOCUMENTS PROVIDED TO PARTICIPANTS

Consent forms describing in detail the study intervention, study procedures, and risks are given to the participant and electronic documentation of informed consent is required prior to starting screener week procedures.

##### 10.1.1.2 CONSENT PROCEDURES AND DOCUMENTATION

All eligible participants identified either by their treating physician or by Deep6 will be contacted by a research coordinator using an IRB approved recruitment email that will explain the study. The patient will be able to reply to the communication with a request to opt-out of further communication. A research coordinator will telephone individuals who do not opt out to discuss their interest in study participation. An IRB-approved script will explain the study in lay language, including the purpose, procedures, and potential risks of the study and research rights as a participant. Study Coordinators will ensure the identity of the person on the phone call is indeed the prospective participant that was intended. REDCap will be used to email the IRB approved electronic consent form to the patient. Participants will have the opportunity to carefully review the electronic consent form and ask questions prior to signing. Participants will complete their consent forms electronically using the 21 CFR 11-compliant online platform, REDCap. A child assent form will be included as part of the informed consent to allow for adolescent participants to be enrolled. Every subject will be informed of the approximate time to complete the consent process. A copy of the informed consent documents will be provided to participants for their records via email. The informed consent will be signed by the patient and the designated investigator before the participant undergoes any study-specific procedures. The rights and welfare of the participants will be protected, and it will be emphasized that their medical care will not be adversely affected in any way if they decline to participate in this study.

All patients will be able to opt-out of the study via email or by phone. We request removal of an official wait time between sending the email/letter and contacting subjects by phone. Our justification is that, to date, in the rural chronic pain study alone, 153 recruitment letters have been sent to Cedars-Sinai patients. However, none of them have contacted our study staff prior to the 7-day period, and of the 33 individuals who were sent a recruitment letter and later declined, only two declined by email. 98.7% of recruitment letters have not obviated the need for a follow-up recruitment call, and this response rate compares to our other trials. Most individuals do not recall seeing or reading the letter when finally reached by phone.

A verbal explanation will be provided in terms suited to the participant's comprehension of the purposes, procedures, and potential risks of the study and of their rights as research participants. Participants will have the opportunity to carefully review the electronic consent form and ask questions prior to signing. The participants should have the opportunity to discuss the study with their family or surrogates or think about it prior to agreeing to participate. The participant will sign the informed consent document prior to starting the screening week surveys. Participants must be informed that participation is voluntary and that they may withdraw from the study at any time, without prejudice.

The informed consent states that any changes in pain management should be made with the participants treating physician.

---

#### 10.1.2 STUDY DISCONTINUATION AND CLOSURE

We do not anticipate any events that would warrant study discontinuation and closure.

---

#### 10.1.3 CONFIDENTIALITY AND PRIVACY

Participant privacy is strictly held in trust by the participating investigators, their staff, and their interventions. Therefore, the study protocol, documentation, data, and all other information generated will be held in strict confidence. No information concerning the study or the data will be released to any unauthorized third party without prior written approval of the sponsor.

Representatives of the IRB or regulatory agencies may inspect all documents and records required to be maintained by the investigator for the participants in this study. The clinical study site will permit access to such records as needed.

Data in the study is collected in three ways: in real-time, at infrequent intervals throughout the study, and through medical record queries. Real-time data, including biometrics and survey data delivered via mobile device, will be stored on secure servers hosted by Amazon Web Services (AWS) and will contain only a unique identifier for each participant. Virtual reality adherence data will also be tracked in real-time and hosted on secure servers by AppliedVR; a separate unique ID will be assigned to each participant. Data collected at infrequent intervals throughout the study, such as entry, 14-day interval assessments, and exit questionnaires will be stored on secure CSMC servers with unique ID's for each participant. Data collected from medical record numbers, such as opioid prescriptions and physician history, will reside on secure CSMC servers and an ID will be assigned to each individual in order to abstract PHI/PII and the medical record number. Each dataset will utilize different unique ID's and a list linking each unique ID to each participant will be stored internally on the secured CSMC network. The linking list allows a researcher with access to the secured files to merge all data using statistical software, while maintaining data confidentiality.

To minimize risk of breaches in confidentiality associated with the access and recording of protected health information, study staff will be assigned unique passwords and usernames to access secure servers. Additionally, identifiable information for participants will be obfuscated using unique ID numbers and a linking list will be held in a secure location.

A detailed list of procedures that protect confidentiality is in section 20.1 of the MOOP.

---

[figure not shown]
#### 10.1.4 FUTURE USE OF STORED SPECIMENS AND DATA

N/A

#### 10.1.6 SAFETY OVERSIGHT

Safety oversight will be under the direction of a DSMB composed of individuals with the appropriate expertise. The DSMB will be appointed by and serve as advisory to the NIAMS. Members of the DSMB should be independent from the study conduct and free of conflict of interest, or measures should be in place to minimize perceived conflict of interest. The DSMB will meet at least semiannually to assess safety and efficacy data on each arm of the study. The DSMB will operate under the rules of an approved charter that will be written and reviewed at the organizational meeting of the DSMB. At this time, each data element that the DSMB needs to assess will be clearly defined. The NIH will provide its input to specify the study sponsor National Institutes of Health staff.

#### 10.1.7 CLINICAL MONITORING

As the intervention in this trial is not greater than minimal risk, a designated member of the study team will conduct periodic monitoring every 6 months and review safety data such as AEs reported, using DSM reports attached in DSMP. The compiled reports will be discussed amongst the study team at the earliest opportunity. These reports will also be submitted to executive secretary and NIAMS via the semiannual DSMB report. The study team will compile with any requested action by the DSMB.

#### 10.1.8 QUALITY ASSURANCE AND QUALITY CONTROL

Our quality assurance (QA) and control (QC) procedures are designed to support adherence to the protocol, obtain complete follow-up data for all participants enrolled, and establish and maintain high standards for validity in collected data ahead of analysis. We approach QA as processes and safeguards for the prevention of data errors, and QC as mitigation efforts reducing impact from errors that have occurred during data capture and/or processing. While much of the QA effort occurs ahead of study launch, both efforts will require real-time and periodic tasks conducted through the duration of the study to ensure consistent checks of data integrity, completeness, and correctness.

QA via error prevention will focus largely on the REDCap system. Before data is entered into REDCap, study personnel will:

- Indicate units in question stems and use field validation whenever possible;
- Define and enforce range minimum/maximum where applicable;
- Ensure uniformity in date formatting across all REDCap date fields;
- Program pre-defined multiple-choice fields whenever possible (as opposed to free text);
- Indicate specific, standardized choices to identify data as intentionally missing (e.g “Not Applicable,” “Don’t Know”) as opposed to blank fields;
- Enforce skip/no-skip logic where appropriate;
- Standardize assignment of raw values. (i.e. if “Yes” is coded as a ‘1’ in one field, it should be coded as ‘1’ in all other project fields); and
- Use case and punctuation consistently across all field labels.

Each aspect of the REDCap data collection system will be tested before actual study data is collected. Study personnel will enter mock data into REDCap forms, serving as the “User” for acceptance testing. We will document the success or failure of a) the user interface for data entry, b) the on-line univariate and range data validation checks, and c) custom functions and coding. This mock data will be exported as SAS/STATA datasets by the research coordinator and subjected to QC procedures.

Our fundamental QC approach prioritizes error detection. Automated QC will occur in a SAS/STATA programming environment and will be tested/iterated on mock data before being employed monthly to exported datasets from both REDCap and the EHR. These QC programs will target potential data anomalies including:

- Missing data or forms;
- Out-of-range or erroneous data;
- Inconsistent, improperly formatted, or out-of-range dates; and
- Fields on a "completed form" not completed.

Once the study begins, routine QC reports will be prepared monthly (with 2 weeks lead-time before proposed monthly uploads to DAC) by the study statisticians. These reports will describe target and actual enrollment, eligibles screened with reasons for screen failure, and participant disposition (enrolled; active, completed, discontinued treatment, and lost to followup). These reports will also provide proportions of forms completed/missing, as well as summaries of problems identified by QC processes. Changes to QC programming will be documented and re-tested for accuracy.

Finally, daily monitoring for data completeness will be undertaken by the study team as a QA effort. Patients will initially be sent a reminder email when they have not submitted data after 2 days. If no response is given two additional 48-hr reminders will be sent. Research staff will attempt to contact the patient up to 3 times in one week.

## 10.1.9 DATA HANDLING AND RECORD KEEPING

### 10.1.9.1 DATA COLLECTION AND MANAGEMENT RESPONSIBILITIES

Study staff will develop, test, and maintain the data capture system using a web-based data collection system, REDCap, as the primary source of data entry and storage. Developed by Vanderbilt University, REDCap is a software toolset and workflow methodology for electronic collection and management of research and clinical trial data. The REDCap system provides a secure, web-based application that is flexible and provides: 1) an intuitive interface for users to enter data and have real time validation rules (with automated data type and range checks) at the time of entry; 2) HIPAA compliant audit trails for tracking page views, data manipulation and export procedures; 3) record locking and electronic signature functions; 4) control over user rights to view and manipulate data; 5) a report builder capable of querying patient records; and 6) automated export procedures for SAS/STATA datasets.

The REDCap system complies with all applicable guidelines to ensure patient confidentiality, data integrity, and reliability. Quality assurance and control procedures will be applied to ensure the completeness, validity, and accuracy of the study database. The MOOP describes data collection processes, database development procedures, quality control processes, and reporting in greater detail.

EHR data will be retrieved by the Research Informatics and Scientific Computing Core (RISCC) at Cedars-Sinai, which facilitates interaction between the research community and the Epic data warehouse and production environment. We will collaborate with RISCC to design queries for portions of participants' records as defined in the data dictionary. The data extracts issuing from these queries will be delivered monthly as CSV files via Box, a HIPAA compliant cloud content management system. These will then be converted to SAS/STATA data sets and subjected to QC procedures in a SAS/STATA environment.

VR device metadata will be provided monthly by AppliedVR as CSV files containing timestamped records of content accessed at the individual device level. These records will feature a device-ID unique to each patient. A linking list containing study-IDs and device-IDs will be stored on a secure server behind the Cedars-Sinai firewall, and only associated with other study data following database lock. In order to monitor weekly adherence, study-staff will access a subset of the metadata limited to study-ID and timestamps of usage. These data will be subjected to QC procedures in a SAS/STATA environment.

Deidentified Fitbit data will be stored by a research-grade, IRB-approved service (Fitabase, San Diego, CA) as minute level data from Fitbit servers for all participants. This data will be retrieved as CSV files and linked to study data in a secure SAS/STATA environment before being subjected to QC procedures.

In order to maintain standard data definitions and structures, the data dictionary and proposed database structures reflect the Standard Clinical Data Interchange Standards Consortium's (CDISC) Study Data Tabulation Model (SDTM). The data elements and relationships described by this standard will facilitate information exchange with DAC. Furthermore, we will employ DAC's forthcoming approach to data cleanliness and completeness standards and notation.

#### 10.1.9.2 STUDY RECORDS RETENTION

In compliance with Protection of Human Subjects regulations, records related to the conduct of this trial, including but not limited to source documentation, informed consent forms, essential study documentation, and documentation of IRB activities, will be retained by the Investigator for a period of 3 years following the official close of the study.

#### 10.1.10 PROTOCOL DEVIATIONS

A protocol deviation is any noncompliance with the clinical trial protocol. The noncompliance may be either on the part of the participant, the investigator, or the study site staff. As a result of deviations, corrective actions are to be developed by the site and implemented promptly.

These practices are consistent with ICH GCP:

- 4.5 Compliance with Protocol, sections 4.5.1, 4.5.2, and 4.5.3
- 5.1 Quality Assurance and Quality Control, section 5.1.1
- 5.20 Noncompliance, sections 5.20.1, and 5.20.2.

Protocol deviations/violations impacting participant safety will be reported to NIAMS and the DSMB Safety Officer through the NIAMS Executive Secretary within 48 hours of the investigator becoming aware of the event; all other deviations/violations that do not impact participant safety can be reported as part of the routine DSMB meeting report. The investigator will also report deviations within 5 working days of identification of the protocol deviation to the IRB. All deviations must be addressed in study source documents and reported to NIAMS. Protocol deviations must be sent to the reviewing Institutional Review Board (IRB) per their policies. The principal investigator is responsible for knowing and adhering to the IRB requirements.

#### 10.1.11 PUBLICATION AND DATA SHARING POLICY

This study will be conducted in accordance with the following publication and data sharing policies and regulations:

This trial will be registered at ClinicalTrials.gov, and results information from this trial will be submitted to ClinicalTrials.gov. In addition, every attempt will be made to publish results in peer-reviewed journals. Data from this study may be requested from other researchers 3 years after the completion of the primary endpoint by contacting the Cedars-Sinai Center for Outcomes Research and Education.

We will also comply with the data sharing policy at NIH under NOT-OD-08-033. We will submit the final manuscripts to the NIH National Library of Medicine PubMed central for archiving upon acceptance for publication.

#### 10.1.12 CONFLICT OF INTEREST POLICY

The independence of this study from any actual or perceived influence is critical. The Cedars-Sinai Identifying and Disclosing Researchers' Financial Interests in Research Policy: Human Research Protection Program requires the Principal Investigator and all members of the study team to disclose their, their spouses'/domestic partners', and dependent children's financial interests in the research regardless of the source of funding. Additional disclosure requirements may apply to investigators involved in Federally-funded research as described in the Cedars-Sinai Management of Industry Relations and Conflicts of Interest Program Policy: Corporate Integrity Program. The Cedars-Sinai Institutional Review Board (IRB) retains authority to determine if the research is allowed to proceed under the terms of the management plan developed by IR/COI considering the potential impact on the process and documentation of informed consent and the equitable selection of subjects. Review of disclosed COIs associated with a human research protocol by IR/COI is requested through submission of the CS-IRB COI Disclosure Form, which details IRB-supported guidelines on methods to manage, mitigate, or eliminate COIs.

## 10.2 ADDITIONAL CONSIDERATIONS

NA

## 11 APPENDIX A: RESEARCH SUPPLEMENT – ADVOCATING FOR UNDERREPRESENTED PATIENT POPULATIONS IN RESEARCH

### 11.1 BACKGROUND AND APPROACH

Black and Hispanic patients are up to five times less likely to have access to digital health information than non-Hispanic whites. In addition to disparities in access and adoption of digital health interventions, there are known disparities in the incidence and reporting of pain by racial and ethnic minorities. This Diversity, Inclusion and Engagement Supplement aims to develop a framework to advance diversity and inclusion efforts for future digital health trials at our medical center and beyond. Further, it will enhance the parent study by seeking to increase the proportion of participants with historically less access to and familiarity with digital technologies while enhancing overall participant racial and ethnic diversity.

#### Approach

The scientific approach of this supplemental grant will be inspired by the **NIH Stage Model for Behavioral Intervention Development (Figure 1)**.

**First**, we will conduct focus groups with non-Hispanic Black and Hispanic patients with cLBP to identify the most important content areas to be included in our two sets of culturally tailored study materials, described below. **Then**, we will employ insights from our patient partners to craft culturally tailored and engaging study materials and will then iteratively optimize the materials through cognitive de-briefing interviews, described below. **Finally**, we will assess whether implementation of culturally tailored study materials leads to a higher proportion of non-Hispanic Black and Hispanic participants when coupled with a novel study-participant cohort building tool, discussed below.

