## 5.5 STRATEGIES FOR RECRUITMENT AND RETENTION

The target sample size is 360. We expect a representative sample of the chronic low back pain patient population seen at Cedars-Sinai. Approximately 58% are female and 42% male. For the first half of the

study, we anticipated patients who identify as white to make up about 76% of the study population, with 12% black or African American, 5% Asian, and 6% who identify as multiracial. Approximately 11% were expected to be Hispanic or Latino. For the second half of the project, per supplementary funding to improve study diversity to better reflect the greater Los Angeles population (see Section 11), we aim to recruit a second-half cohort to be 35% non-Hispanic white, 17% non-Hispanic black, and 40% Hispanic. We expect to randomize 10 participants per month over 36 months.

Prospective participants will be referred by physicians at the designated clinical sites or identified using the Deep 6 AI® cohort building software, which uses natural language processing to search the Cedars-Sinai EHR for patients who meet the study's inclusion and exclusion criteria. We anticipate screening 800 potential participants in order to randomize 360. Recruitment of women is not expected to be a problem, because patients seeking care for cLBP are disproportionately female. Women who are pregnant or planning to become pregnant are not excluded from participating. Race and ethnicity of enrolled participants will be tracked monthly. If the proportion of minority participants appears to be lagging, the number contacted will be increased.

Eligible potential participants will be sent an IRB- approved recruitment letter explaining the study via email. For individuals identified via cohort builders who have seen a physician partnered with the study staff, a personalized letter bearing their treating physician's voice and signature will be used; all other cohort builder identified individuals will be sent a letter from the primary investigator. An informational study brochure will also be attached. The recipient may opt-out of further contact by replying to the email.

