## **Aim 2. Oversample non-Hispanic Black and Hispanic participants in parent study using a cohort building tool housed within the electronic health record (EHR).**

After developing two sets of culturally tailored study materials, we will next seek to deliver those materials to eligible study participants. This, in turn, will require us to identify enough non-Hispanic Black and Hispanic participants with cLBP to meet our target goals, described later in this section. To achieve this aim, we will employ Deep6 AI® (Pasadena, CA), a natural language processing (NLP) cohort building tool, and enlist Cedars-Sinai’s Enterprise Information Services (EIS), to oversample non-Hispanic Black and Hispanic participants from throughout Cedars-Sinai and our participating recruitment sites. Deep6 specifically integrates with our EHR to search both structured and unstructured data to build cohorts for clinical trials, and EIS will conduct SQL queries based on exclusionary criteria, race and ethnicity, and visits with recruiting physicians to capture additional participants not included in the Deep6 sample. Although Deep6 is already part of our protocol, it is not currently being used to specifically target study

participants by race or ethnicity. Further, it can only provide a maximum of 7,500 qualifying patients per pull. In this supplement, we will oversample target populations using Deep6 and EIS, then deliver the appropriate set of tailored recruitment materials developed in Aim 1 to these identified prospective participants. We will monitor outcomes by comparing actual recruitment against target oversampling goals, as discussed, below.

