### 11.4 STRATEGIES TO ENSURE TARGETS ARE MET

**Monitoring Recruitment Progress:** The research team will meet weekly during the study to monitor progress towards achieving target goals and will track progress using tables and visual dashboards. If the performance line falls below the target line for three consecutive weeks, then we will initiate a three-pronged strategy to course-correct as needed:

Strategy 1—Adjust Deep6 and EIS search algorithms and sample rates: If recruitment tracking reveals projections that we are falling short of target goals, then we will consult with Deep6 NLP and EIS specialists to fine-tune the parameters of the search algorithm. For example, if race/ethnicity fields are inaccurate or incomplete for some records, there may be other viable approaches such as NLP searches of clinician-inputted text within notes indicating race or ethnicity. Further, if we find specific groups are disproportionately unable to complete the screening process, we will further oversample the ratio of these participants contacted within the cohort builder lists to ensure enrollment rates meet our new target proportions.

Strategy 2—Interviews of non-enrolled patients: If necessary, we will seek consent to interview non-Hispanic Black and Hispanic patients who were invited to participate in the study, received the tailored recruitment materials, but nonetheless opted not to enroll in the trial. We will conduct individual cognitive debriefing interviews using the same techniques described under Aim 2, but here focus on individuals who experienced the recruitment materials first-hand. We will update recruitment materials further if these interviews elicit specific and actionable feedback that is incremental to the Aim 1 results.

Strategy 3—Interviews of patients who withdrew from the study: In addition to interviewing patients who declined to enroll, we will also seek consent to interview non-Hispanic Black and Hispanic participants who enrolled in the study but later dropped out before completion despite receiving tailored post-enrolment materials. These study participants may have a different

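### Appendix A cannot tell whether the tailored materials raised Black and Hispanic enrolment: its only measure, enrolled share against target, is one that staff steer through whom they contact.

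*Protocol*

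**What the plan says.** Section 11.1 of the protocol (Approach) states the question: "we will assess whether implementation of culturally tailored study materials leads to a higher proportion of non-Hispanic Black and Hispanic participants". The same sentence then adds a qualifier, namely that this is to be judged "when coupled with a novel study-participant cohort building tool". The verb is causal and its subject is the materials, but the question as posed covers materials and tool together.

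Section 11.2, Aim 2, gives the only method of evaluation: "We will monitor outcomes by comparing actual recruitment against target oversampling goals". It also describes how candidates are found. Before the supplement Deep6 did not select people on race or ethnicity; in the protocol's words, "it is not currently being used to specifically target study" members on that basis. Under the supplement, "we will oversample target populations using Deep6 and EIS, then deliver the appropriate set of tailored recruitment materials developed in Aim 1".

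Section 11.3 starts the new materials and the new strategies together, once half the cohort is randomised. The targets for the second half are 17% non-Hispanic Black (previously 12%), 40% Hispanic (previously 11%) and 35% non-Hispanic white (previously 76%).

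Section 11.4 sets a trigger for corrective action: "If the performance line falls below the target line for three consecutive weeks". One of the actions, for groups that disproportionately fail to complete screening, is that "we will further oversample the ratio of these participants contacted within the cohort builder lists to ensure enrollment rates meet our new target proportions". Section 5.5 has a related rule for the whole trial: "If the proportion of minority participants appears to be lagging, the number contacted will be increased".

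Appendix A specifies no comparison with untailored materials, no randomisation of materials and no enrolment rate per person contacted. The SAP does not cover the supplement.

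**The concern.** An enrolled share depends on two things: how many people of each group are contacted, and what fraction of those contacted enrol. The materials can act only on the second. Staff set the first directly, change it on the same date as the materials, and may change it again if the share falls short. A poor response to the materials can thus lead to more contacts, which restores the share and hides the poor response.

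At stake is what the supplement may conclude. Section 11.1 aims at a framework for diversity efforts in later digital health trials at the centre and elsewhere. If a rise produced by oversampling is read as an effect of the tailored materials, other trials may spend effort on materials whose contribution was never measured.

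**Working it through.** The plan gives no test, significance level, sample size or effect size for this assessment, so there is no stated figure to reproduce. The check asks what the enrolled share can show about the materials.

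**Inputs** (sections 5.5 and 11.3)
- Target for the first half: 12% Black + 11% Hispanic = 23%, leaving 77% other. Section 11.3 names the 12% as the previous target for non-Hispanic Black participants, so the two are treated as not overlapping.
- Target for the second half: 17% + 40% = 57%, leaving 43% other.

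Both are targets. Section 11.3 says that the 11% Hispanic goal was being met, but gives no observed mix.

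**Identity.** Let c be the share of contacts who are Black or Hispanic, and let r be their enrolment per contact divided by that of everyone else. Then

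enrolled odds = [c / (1 − c)] × r

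and, from first half to second,

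enrolled odds ratio = contact odds ratio × (r in second half / r in first half).

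**No effect of the materials.** The enrolled odds ratio needed is (0.57/0.43) / (0.23/0.77) = 1.326 / 0.299 = 4.44. If the materials do nothing, r is unchanged and cancels, so a contact odds ratio of 4.44 gives the whole rise. This holds at any constant r.

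**Contact mixes that enrol exactly 17/40/43** (Black/Hispanic/other, %). The documents give no relative yield by group, so r is an assumption and is varied.

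| r, first half → second half | Contact mix, first half | Contact mix, second half |
|---|---|---|
| 0.5 → 0.5 | 19.5/17.9/62.6 | 21.7/51.0/27.4 |
| 1.0 → 1.0 | 12/11/77 | 17/40/43 |
| 1.5 → 1.5 | 8.7/7.9/83.4 | 14.0/32.9/53.1 |
| 1.0 → 0.8 (materials harm) | 12/11/77 | 18.6/43.8/37.6 |

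For the last row, the weights are 0.17/0.8 = 0.2125, 0.40/0.8 = 0.500 and 0.43. Their sum is 1.1425, and dividing by it gives the mix. The contact odds ratio needed is 4.44/0.8 = 5.55.

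**The materials alone.** With the contact mix unchanged, relative yield would have to rise by a factor of (0.17/0.12)/(0.43/0.77) = 2.5 for Black candidates and (0.40/0.11)/(0.43/0.77) = 6.5 for Hispanic candidates to reach the targets.

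The same enrolled share, exactly on target, thus follows from materials with no effect, with a 20% loss of yield, or with a large gain. The share does not distinguish them.

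**The case against.** The strongest reply is that the stated question concerns a package. It includes the cohort-building tool, Aim 2 is openly an oversampling aim, and section 11.4 is about reaching targets. For that package the enrolled share is a coherent outcome. This stands. A reader might infer that Appendix A promises a test of the materials in isolation, and it does not. What remains is that the sentence makes the materials the thing that leads to the higher share, and no measure is offered that could show they contributed.

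Three other strong readings also go too far.
- A reader might speak of a false-positive rate. The documents plan no significance test and no before-and-after comparison of shares. Simulating such a test at 23% and 57% would show only that these two figures differ.
- A reader might say that contact ratios rise whenever enrolment lags. Section 11.4 needs three consecutive weeks below the line, its further-oversampling clause is tied to groups that disproportionately fail screening, and its other two strategies are interviews that may lead to revised materials. Section 5.5 does have a looser rule on numbers contacted.
- A reader might say that the rise is guaranteed. It can appear without help from the materials, provided that enough eligible candidates can be found.

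It is also fair that the materials have an evaluation of their own, the cognitive debriefing in Aim 1. That addresses clarity and appropriateness, not enrolment. Appendix B models enrolment on patient-level variables but names no term for the materials, so it does not fill the gap.

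**Conclusion.** The point holds in a limited form. Meeting the second-half targets would show that the combined package recruited the intended mix. It would not show that the tailored materials contributed, because contact odds about 4.4 times higher give the full move from 23% to 57% with no effect of the materials.

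That figure rests on using the two sets of targets as the before and after shares, on Black and Hispanic being non-overlapping in the first-half targets, and on relative yield staying constant. It does not depend on the level of that yield. The actual contact mixes are not in the documents.

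The consequence is confined to the supplement. A reader might infer that the trial's efficacy results are weakened, but who is contacted is settled before randomisation, and the comparison between VR arms does not rest on this assessment. The change is worth making because it is cheap and alters what the supplement can claim.

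**What to change.** **Wording.** In sections 11.1 and 11.2, state that enrolled share against target is recruitment performance of the combined package and will not be credited to the materials.

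**Analysis, if anything is to be said about the materials.** Take everyone sent a recruitment letter as the denominator and randomised (yes/no) as the outcome. Fit a logistic model with group (non-Hispanic Black, Hispanic, non-Hispanic white), period (before or after the switch) and their interaction. The interaction compares the change in yield in each target group with the concurrent change among non-Hispanic white candidates. Report numbers contacted and randomised by group and period beside it.

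**Cost and limits.** No new patients or visits are needed.
- First-half denominators by race and ethnicity must be recovered from the EHR. Deep6 was not targeted by race or ethnicity before the supplement, and section 11.4 allows that these fields may be inaccurate or incomplete. Section 5.4 collects race and ethnicity from participants, not from everyone sent a letter.
- The comparison stays observational. The amendment history also lists the treating-physician letter (version 6.1) and removal of the 7-day wait (version 6.3). The white control group removes such changes only if they act equally on all groups.
- Yield per letter says nothing about the tailored post-enrolment items, such as the instructions for the hardware and software.
- The result may be less favourable than the enrolled share.

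If the first-half denominators cannot be recovered, limit the conclusion to the package.
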